7.2.2 Visit 2 or Day 2 or Post-test, etc. (If applicable)

Provide a description of what procedures will be performed on visit 2 or day 2 or post-test in order of how these will be done. If your study involves more than two sessions or visits replicate this section for each additional session or visit (e.g., 7.2.3, 7.2.4, etc.). If your study involves only one session or visit, delete this section.

Aim 1:

Visits 2-6: After the intervention starts, we will measure agitation, BPSD, affect, and sleep, and intervention-related adverse effects using the CMAI, NPI-NH, ARS, PSQI, and adverse effect checklist once every two weeks.

Aim 2:

Visits 2-6: After light is installed, we will monitor the lighting by 1) on-site manual light measurements twice a week for 13 weeks, and 2) a personal light monitor, LYS button, placed on participants, all day, 7 days a week, every two weeks for 13 weeks.

7.3 Duration of Participation

Describe how long subjects will be involved in this research study. Include the number of sessions and the duration of each session - consider the total number of minutes, hours, days, months, years, etc.

Aims 1 and 2: Residents

The study lasts 13 weeks with baseline data collection: one week for baseline, four weeks for intervention (SABL), two weeks for post intervention/washout period, four weeks for control, and two weeks for post control. The baseline survey of the residents regarding cognitive function and agitation may take 10 minutes to complete.

Aim 3: Staff and administrators 1-2 visits for a total of 1-2 hours. The surveys will take approximately 10-15 minutes to complete, and the interview will take about 1 hour.

7.4 Test Article(s) (Study Drug(s) and/or Study Device(s))

7.4.1 Description

Provide a brief description of all test articles (drugs (including any foods and dietary supplements), devices and/or biologics) used in the research including the purpose of their use and their approval status with the Food and Drug Administration (FDA). Include information about the form of the drug product (e.g., tablets, capsules, liquid).

The SABL system has a pre-programmed 24-hour control schedule on illuminance settings to mimic the natural bright-dark cycle. While research evidence suggests the potential positive effect of the lighting intervention on people with dementia, the lighting device being used in this research is not currently FDA approved for the use of improving behavioral symptoms of dementia. It will regularly monitor the lighting level using customized photosensors and automatically adjust the lights to accommodate the daylight effect, minimizing staff burden and maintenance efforts, while maximizing the LI effect. Our proposed SABL will provide bright light with illuminance targeted at 400 lux and CS ≥ 0.3 at the eye level, and dim light ≤ 40 lux and low CS ≤ 0.1 at night to maintain a bright-dark cycle to regulate activity/rest rhythm, improve sleep, and reduce agitation. We will measure the light levels received by each participant using a personal, wearable lighting measure device, LYS button, and will use the actual dosage (lux and CS levels) received by participants to analyze the intervention effect.

The lighting intervention, SABL, design and installation will involve five phases:

1) **Developing an implementation protocol.** PIs [name] and [name] will set up an advisory board at each NH that includes a certified nursing assistant (CNA), a nurse, the director of nursing (DON), the director of maintenance (DOM), and the administrator (NHA). Through the advisory board, we will obtain input from NH stakeholders about implementation procedures. Next, we will develop a protocol that lists the workflow, key steps, and associated personnel customized to each facility. [name] will work with the DOM at each facility to finalize the plan for SABL installation and maintenance and to ensure the installation follows NH regulations.

2) **Observing resident routines and preference to tailor SABL design.** We will observe each participant, in terms of their daily routine, activities, and habitual behaviors on 2 weekdays and 1 weekend day and fine tune the lighting intervention design. In addition, switches and wireless dimmers will be supplied in case residents or staff need to manually override the lighting conditions. The pre-programmed settings will be auto-resumed after

1 hour.

3) **Measuring and simulating the existing daylighting.** Using lighting simulation software, PI [name] will develop a digital model, including accurate building models, local weather files, and interior design to predict the indoor daylight distribution.

4) **Designing and simulating the SABL.** Lighting distribution, with selected sources and shields, will be designed by conducting a series of computational simulations to avoid unwanted lighting penetration to non-participants' use areas.

5) **Installing the SABL system.** The system will be integrated into the existing electrical systems by replacing existing light sources (e.g., bulbs, tubes) without incurring labor costs for installation, disruption to the facility's operation, or inconvenience to residents and staff. New stable floor-standing luminaires may be added only if the light source replacements on existing luminaires are not able to meet the design levels.

7.4.2 Treatment Regimen

Describe dose, route of administration and treatment duration. Include information about dose adjustments.

The SABL system includes tunable LED lights, photosensors, and controllers and will be installed by replacing the bulbs of the existing fixtures. The SABL will provide bright light targeted at 400 lux and CS \geq 0.3 in participant bedrooms and designated areas in the dining room and activity room during the day and provide dim light \leq 40 lux and CS \leq 0.1 in participant bedrooms at night. The intensity and color of our SABL will be perceived like low-level daylight and does not cause glare.

We estimate each resident will be exposed to the bright light for at least 4 hours per day (2 hours during three mealtimes and 2 hours during other daily activities). The photosensors will continuously monitor daylight situations and adjust accordingly. It is possible that participants may receive >400 lux and CS >0.3 from daylight. However, based on the on-site measurements and observations, it is unlikely participants will receive overly high lighting conditions.

7.4.3 Method for Assigning Subject to Treatment Groups

Describe the randomization process and how the associated treatment assignment will be made.

The study design is a crossover, cluster randomized controlled trial. We plan to conduct the study in two nursing homes. The study procedures include five phases over 13 weeks (Table). The two NHs will be randomly assigned into different sequences for intervention and control. Otherwise, the same study procedures will be conducted simultaneously at the two nursing homes. During the daytime, participants will be guided and encouraged to spend time in the designated areas in the dining room and activity room for their meals and daily activities.

Table. Intervention testing procedures and timeline.

Week	1	2	3	4	5	6	7	8	9	10	11	12	13
------	---	---	---	---	---	---	---	---	---	----	----	----	----

Study phases	NH A	Baseline	Intervention		Post intervention/washout		Control			Post control	
	NH B		Control		Post control/washout		Intervention			Post intervention	
Lighting	Usual light		I: SABL C: Usual light		Usual light		C: Usual light I: SABL			Usual light	
Data collection	Baseline, L&E		L&E	L&E		L&E		L&E	L&E		L&E

L=lighting measured via individual light monitor, E=effect outcomes (e.g., agitation, BPSD, affect, and sleep) and adverse effects

7.4.24 Subject Compliance Monitoring

Insert the procedures for monitoring subject compliance.

Each participant will wear the personal light monitor, LYS Button (Figure) to measure lighting intensity (lux) and CS level received. The data will be used to further calculate participants' hours of intervention exposure per day.

Lighting will be measured once every 10 minutes, all day, 7 days a week, every other week over the 13-week study period. The monitor is small (1 inch), lightweight (4g), and user-friendly and will be placed on participants' shirt collar or shoulder.

Figure . Light Monitor LYS Button

In addition, the light monitor enables real-time remote checking. [name] will pre-set a series of algorithms determining the device use status. If the device appears not to be placed or functioning properly (e.g., lighting data remains completely unchanged for over 1 hour during daytime), the system will send a warning message to the team (including [name] and [name]). We will make all attempts to check the device on site.

7.4.25 Blinding of the Test Article

Describe how the test article is blinded.

For blinding purposes, prior to the control period, we will perform the lighting installation procedure, similar to the intervention period, though with baseline/non-SABL light bulbs, to blind the research assistants who collect data, participants, and nursing home staff. Also, we will provide minimal details about the study design and lighting condition sequence. In statistical analysis, diagnostic analyses will be carried out to examine underlying assumptions, detect any violations, and identify the most appropriate modeling approach.

7.4.26 Receiving, Storage, Dispensing and Return

7.4.26.1 Receipt of Test Article

Describe how the test article will be obtained and from what source.
Describe how the study test article will be packaged along with amounts (e.g., number of tablets/capsules or volume of liquid) and labeling. If drug kits are used, describe all the contents of the kit and associated labeling.

[name] will purchase and design the lighting system, including

the tunable LED lights, photosensors, and controllers. The SABL system will be integrated into the existing electrical systems by replacing existing light sources (e.g., bulbs, tubes). New stable floor-standing luminaires may be added only if the light source replacements on existing luminaires are not able to meet the design levels. [name] will work with the nursing home director of maintenance (DOM) to install the lighting system.

The lighting dosage will target at 400 lux and CS=0.3 during the day and provide dim light \leq 40 lux and CS \leq 0.1 in participant bedrooms at night. The intensity and color of our SABL will be perceived like low-level daylight and does not cause any glare. We estimate each resident will be exposed to the bright light for at least 4 hours per day (2 hours during three mealtimes and 2 hours during other daily activities). The photosensors will continuously monitor daylight situations and adjust accordingly. It is possible that participants may receive $>$ 400lux and CS $>$ 0.3 from daylight.

7.4.6.2 Storage

Describe the plans to store, handle the test article so they will be used only on subjects and only by authorized investigators. Describe storage temperature requirements and how temperature will be monitored and recorded.

[name] will be responsible for storing and handling the lighting related equipment. He may work with nursing home director of maintenance (DOM) and designated research team member to handle the lighting system. Only authorized researchers will handle the lighting system, including transporting and installing it in the site.

7.4.6.3 Preparation and Dispensing

Describe how the test article will be assigned to each subject and dispensed. Describe the steps necessary to prepare the test article. Include where the test article preparation will be done and by whom. Fully describe how the study treatment is to be administered and by whom.

In preliminary measures, the average nursing home lighting is 250 (\pm 105) lux in bedroom, 193 (\pm 122) lux at corridor, 170-288 (\pm 106-123) lux at the dining room, and 285 (\pm 91) lux. The measures are consistent with a prior study showing that the lighting in nursing homes is largely insufficient to meet the visual needs to older adults (De Lepeleire et al., 2007).

In this study, the lighting dosage will target at 400 lux and CS=0.3 during the day and provide dim light \leq 40 lux and CS \leq 0.1 in participant bedrooms at night. The intensity and color of our SABL will be perceived like low-level daylight and does not cause any

glare. We estimate each resident will be exposed to the bright light for at least 4 hours per day (2 hours during three mealtimes and 2 hours during other daily activities). The photosensors will continuously monitor daylight situations and adjust accordingly. It is possible that participants may receive >400lux and CS>0.3 from daylight.

7.4.6.4

Return or Destruction of the Test Article

Describe the procedures for final reconciliation of the test article supply at the end of the study and whether the test article is to be shipped back to a source or destroyed on site.

[name] and his designated research assistant will collect the lighting system at the end of the study and bring it back to the lab.

7.4.6.5

Prior and Concomitant Therapy

Describe what prior and/or concomitant medical therapy will be collected. Describe which concomitant medicines/therapies are permitted during the study. Describe which concomitant medicines are not permitted during the study.

No prior or concomitant medical therapy will be provided or prohibited.

8.0 Number of Subjects and Statistical Plan

8.1

Number of Subjects

Indicate the maximum number of subjects to be accrued/enrolled, to include all persons who sign consent for the study. If applicable, distinguish between the number of subjects who are expected to be enrolled and screened, and the number of subjects needed to complete the research procedures (i.e., numbers of subjects excluding screen failures.)

Aims 1 and 2: Residents

Resident: The target sample size is 40 nursing home residents. We expect to screen 80 potential residents to identify and enroll 40 eligible residents.

Aim 3: Staff and Administrators

Staff: We plan to enroll 16 NH staff/administrators, including three CNAs, one activity staff, one nurse, one DON, one DOM, and one NHA.

8.2

Sample Size Determination

If applicable, provide a justification of the sample size outlined in section 8.1 to include reflections on, or calculations of, the power of the study.

Aims 1 and 2: Residents

We will recruit 40 residents with ADRD and agitation, 20 from each NH. The two NHs have at least a floor or a wing that is primarily dedicated to residents with ADRD, where we plan to

install the lighting and carry out the study. As attrition is expected to be around 10%, based on prior studies with a similar population, this will result in a final sample size of 36. This sample size was calculated based on a significance level of $\alpha=.05$, medium effect size Cohen's $d=0.53$, reported in previous studies, power=0.92.

Aim 3: Staff and Administrators

CNAs, activity staff, and nurses provide the most direct care. Priority will be given to individuals who provide care for resident participants. DONs, DOMs, and NHAs are decision makers for intervention implementation. The DOMs can provide feedback on the feasibility of installing and maintaining the lighting system and ensure the installation follows NH regulations.

Potential participants will be initially identified by NH staff and confirmed by the research team. Sample size may be increased to reach data saturation.

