7.1 Study Design

Describe and explain the study design.

Aim 1: Pilot test the effect of SABL in reducing agitation in persons with dementia. This is a crossover, cluster randomized control trial to pilot test the effect of SABL in NHs. This design includes a 4-week intervention period and 2-week washout period. This design will allow for participants to act as their own control and thus reduce the needed sample size and strengthen the research rigor. The study procedures include five phases over 13 weeks. We will recruit a total sample of 40 nursing home residents with dementia and agitation from the 2 nursing homes, 20 residents from each nursing home. The two NHs will be randomly assigned into different sequences for intervention and control. Otherwise, the same study procedures will be

conducted simultaneously at the two NHs. During the daytime, participants will be guided and encouraged to spend time in the designated areas in the dining room and activity room for their meals and daily activities. For blinding prior to control period, we will perform installation procedures with non-SABL light bulbs. We will evaluate the effect of SABL on agitation, other BPSD, affect, and sleep, based on the actual lighting levels participants receive measured by personal light monitors. The study procedures include five phases: 1) baseline, 2) intervention, 3) post intervention/washout, 4) control, and 5) post control/washout. The sequence of intervention and control differs between the two NHs based on randomized assignment. Agitation and lighting will be measured at baseline and then once every two weeks throughout the study. We hypothesize that participants will show less agitation during and after SABL compared to baseline and control periods. We will also explore the intervention effect on other BPSD and affect and monitor adverse effects. **Aim 2: Evaluate the fidelity of the SABL delivery.** We will evaluate the fidelity of SABL delivery by measuring lighting intensity (lux) and CS levels in two ways: 1) on-site light measurements, and 2) a personal light monitor. The actual lighting data will be compared to the intended SABL design.

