Four strategies will be implemented to ensure the actual lighting condition the SABL delivers is as designed. First, SABL system has a pre-programmed 24-hour control schedule on illuminance settings to automatically maintain the target lighting dosage. The SABL include photosensors to measure the lighting every 10 minutes and will automatically adjust tunable LED lights through wireless communication to accommodate the daylight effect. Second, the wall-mounted photosensors can detect any problematic lighting events (e.g., <400lux or CS<0.3 during the day) in real-time and will trigger alerts to the research team for trouble shooting. Third, a comprehensive in field lighting measurement will be performed by the research team twice a week during the intervention and control periods to confirm the designed conditions and address any lighting system issues. Fourth, we will remotely monitor the lighting data from the personal light monitors and then analyze the daily data during the data collection week to detect any individual compliance issues and potential device or lighting problems.

The following will describe the installation of SABL system.

First, the SABL system will be installed in resident participants' bedrooms, and designated areas in the hallways, dining rooms, and activity rooms to cover areas that resident participants usually spend time with. Specifically, in the dining room and activity room, the lighting system will only cover the participating residents' tables and areas where they sit. Note that residents and staff typically only spend minimal time in hallways. As a check, prior to installation, the SABL system will be verified via the computer simulation in a lab setting to ensure it only covers the designed areas for participants.

Second, prior to the study, we will announce the general timeline of the study period and will post signs in the dining rooms and activity rooms to notify people that lighting interventions are taking place. While nonparticipants and staff are not restricted from entering the rooms with SABL lighting, they can opt out of the specific areas in the rooms with SABL if they prefer. Non-participating residents will be informed the research areas and the priority of the areas will be given to participants.

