8.3 Statistical or Analytic Methods

Describe the statistical methods (or non-statistical methods of analysis) that will be employed.

Aim 1

All data will initially be assessed with descriptive techniques to determine distributions and identify outliers. Baseline to post-intervention changes in participants' CMAI, NPI-NH, and ARS scores will be used as the outcomes in all subsequent analyses. To conduct the group analysis, each participant will serve as their own control, which allows minimal use of control variables. The effect of the intervention will be analyzed using multi-level modeling to adjust for clustering of participants at the facility level. We will use the daytime and nighttime average of lighting dosages (lux and CS) from the personal light monitors as the independent variable to analyze the effect of SABL on changes in CMAI, NPI, and ARS. Although not powered for a detailed analysis, we will explore the impact of participant characteristics (sex, age, race, ethnicity, ADRD stage, and daylight exposure) on the intervention effect by adding them as covariates to the regression model.

Aim 2

All data will initially be assessed using descriptive techniques to examine underlying assumptions and detect any violations. To assess the intervention fidelity, the lux and CS data measured via manual measurements will be analyzed using one sample t-tests to analyze lighting levels during the day and nighttime, compared to the target levels. The data from personal light monitors will be analyzed similarly at individual level. Although not powered for a detailed analysis, we will explore the impact of participant characteristics (e.g., sex, age, race, dementia stage, comorbidity, facility, and daylight conditions) on the lighting received based on the personal light monitor.

Aim 3

Quantitative Analysis: The data include ratings of acceptability, feasibility, appropriateness, time, and cost of installing and maintaining the intervention. All data will be analyzed using descriptive analyses. Although not powered for a detailed analysis, we will explore differences in perceptions of intervention feasibility and acceptability between sexes as well as the difference across professional roles and between facilities.

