Study Title: The Effect of Smart Ambient Bright Light for Nursing Home Residents with Alzheimer's Disease and Related Dementias (Smart Lighting Study)

PIs: [name] (Contact PI) and [name]

NCT05825404

04-24-2023

Data Analysis Plan

Aim 1: Pilot test the effect of SABL in reducing agitation in ADRD.

All data will initially be assessed with descriptive techniques to determine distributions and identify outliers. Baseline to post-intervention changes in participants' CMAI, NPI-NH, and ARS scores will be used as the outcomes in all subsequent analyses. To conduct the group analysis, each participant will serve as their own control, which allows minimal use of control variables. The effect of the intervention will be analyzed using multi-level modeling to adjust for clustering of participants at the facility level. We will use the daytime and nighttime average of lighting dosages (lux and CS) from the personal light monitors as the independent variable to analyze the effect of SABL on changes in CMAI, NPI, and ARS. Although not powered for a detailed analysis, we will explore the impact of participant characteristics (sex, age, race, ethnicity, ADRD stage, and daylight exposure) on the intervention effect by adding them as covariates to the regression model.

Aim 2: Evaluate the fidelity of the SABL delivery.

All data will initially be assessed using descriptive techniques to examine underlying assumptions and detect any violations. To assess the intervention fidelity, the lux and CS data measured via manual measurements will be analyzed using one sample t-tests to analyze lighting levels during the day and nighttime, compared to the target levels. The data from personal light monitors will be analyzed similarly at individual level. Although not powered for a detailed analysis, we will explore the impact of participant characteristics (sex, age, race, ADRD stage, co-morbidity, facility, and daylight conditions) on the lighting received based on the personal light monitor.

Aim 3: Evaluate the feasibility of implementing SABL.

The data includes ratings of acceptability, feasibility, and appropriateness. All data will be analyzed using descriptive analyses.

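### The stated power of 0.92 fits a paired mean-change test and was not derived for the light-dose model that Aim 1 specifies

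*Protocol*

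**What the plan says.** Protocol section 8.2 sets the target: "We will recruit 40 residents with ADRD and agitation, 20 from each NH". It expects about 10% attrition, which leaves 36, and quotes alpha .05, a Cohen's d of 0.53 and "reported in previous studies, power=0.92". It does not name the test, the sidedness, or whether d is a paired or a between-group d. Section 7.1 gives the design rationale: "This design will allow for participants to act as their own control and thus reduce the needed sample size".

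For the Aim 1 analysis, the SAP (in the same terms as Protocol section 8.3) fixes the outcome: "Baseline to post-intervention changes in participants' CMAI, NPI-NH, and ARS scores will be used as the outcomes in all subsequent analyses". Section 8.3 then names the regressor: "We will use the daytime and nighttime average of lighting dosages (lux and CS) from the personal light monitors as the independent variable". The model is multi-level, and facility is the only clustering level named. Residents are said to be their own controls, but no condition indicator, period term or resident effect is listed, and nothing says whether control-period data enter the dose model. The caveat about limited power is attached only to the exploratory participant characteristics.

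**The concern.** A standardised mean difference is the effect size for a mean contrast. It is not the effect size of a regression slope on light dose, and the plan gives no slope, correlation or spread of dose from which to power one. On the more literal reading of section 8.3, each resident supplies one change score, which is regressed on that resident's average light. The slope is then estimated only from differences in dose between residents. A benefit shared equally by all residents would go into the intercept and would not be tested. SABL could work at exactly the assumed size and the slope could still be non-significant, in a trial described as having 92% power. This issue is separate from clustering, sidedness and the scale of d: it would remain with independent residents and a paired d.

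**Working it through.** **Inputs from section 8.2:** alpha 0.05, d=0.53, 40 enrolled, 10% attrition, 36 final, power 0.92. Check: 40 × 0.90 = 36.

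**1. Reproducing 0.92.** For a paired or one-sample test of a mean change, the noncentrality is d√n.
- n=36: 0.53 × 6 = 3.18. Two-sided, the normal approximation is Φ(3.18 − 1.96) = 0.889 and the noncentral t gives 0.871. One-sided: 0.938 and 0.930.
- n=40: 0.53 × 6.325 = 3.352. Two-sided: Φ(3.352 − 1.96) = 0.918 and 0.905. One-sided: 0.956 and 0.950.
- Two independent groups, two-sided: 0.356 with 18 per group, 0.388 with 20, 0.614 with 36, 0.659 with 40.

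So 0.92 fits a paired mean change, either two-sided at the enrolled n or one-sided at the final n. It does not fit a two-group comparison. That the calculation was paired is an inference from this match, supported by the own-control rationale in section 7.1.

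**2. Dose slope across residents (one change per resident).** Assumptions: n=36 independent residents; effect proportional to the dose increment; mean SABL effect 0.53 of the total SD of change; dose measured without error; two-sided alpha 0.05. CV is the between-resident SD of the dose increment divided by its mean. The documents do not give it, so a range is shown. The implied correlation of change with dose is r = 0.53 × CV. Power is by simulation.

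| Assumed CV | r | Power, n=36 |
|---|---|---|
| 0.25 | 0.133 | 0.12 |
| 0.5 | 0.265 | 0.35 |
| 0.7 | 0.371 | 0.62 |
| 0.8 | 0.424 | 0.75 |
| 1.0 | 0.530 | 0.93 |

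Adjusting for facility lowers these by at most about 0.015. By Fisher z, the detectable correlation is tanh[(1.96 + 0.84)/√33] ≈ 0.45 for 80% power. For 92% power it is about 0.53, which corresponds to a CV of about 0.53/0.53 = 1.0.

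**3. Dose slope within resident (SABL and usual-light periods both modelled).** Each resident's difference in change between periods is regressed on the difference in dose, with the same effect scaled by the SD of that difference. Power at n=36, two-sided, is 0.87 at a CV near 0, 0.89 at 0.25 and 0.94 at 0.5. Adding a period term leaves these essentially unchanged (0.87, 0.90, 0.94).

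All figures ignore the uncertainty from having only two facilities, error in the light monitors, and multiplicity over four dose measures (day and night, lux and CS) and three outcome scales.

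**The case against.** The strongest case on the other side is that the plan need not be read as an across-resident slope. The design is a crossover, the hypothesis in section 7.1 compares SABL with both baseline and control periods, and light and outcomes are collected at seven visits per resident under both lighting conditions. Section 8.3 also calls residents their own controls. On that reading dose varies mainly within resident and power is not lost. This stands as a possible intention. It does not settle the text, because a change from baseline already makes a resident his or her own control, and no resident or period term is named.

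A reader might infer that the true power of the Aim 1 analysis is far lower than 0.92. The documents do not support that as a flat statement, since it needs both the across-resident reading and a dose CV clearly below 1. Nor does converting d=0.53 to a correlation settle the size: the usual conversion is for two equal independent groups, which is not the calculation that reproduces 0.92.

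A reader might also infer that because the system is built to "automatically maintain the target lighting dosage", the spread of dose must be very small. The target governs the fixtures, whereas the regressor is light at the resident. Starting levels differ: section 7.4.6.3 gives 250 (±105) lux in bedrooms and 193 (±122) in corridors against a 400 lux target, so 105/150 = 0.70 and 122/207 = 0.59. These are SDs for locations, not residents, and serve only as a rough guide. Time in lit areas, manual override and daylight add further variation.

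Finally, no passage says that a null slope would be taken as no SABL effect, and Aim 1 is a pilot. That risk of misreading is a reason for clear wording; it is not something the plan commits to.

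**Conclusion.** The point holds in a limited form. The power of 0.92 matches a paired mean-change test and was not derived for the dose model that section 8.3 and the SAP specify. At the stated final n of 36, even the paired test has two-sided power of 0.87 to 0.89, so 0.92 requires either all 40 residents or a one-sided test.

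Whether power is lost depends on which data enter the model, and the plan does not say. With one change per resident, power runs from about 0.12 to 0.93 for an assumed CV from 0.25 to 1.0, under the linear, error-free, independent-resident assumptions above. With both periods modelled within resident, it is about 0.87 or more. The defect is a power statement not tied to the specified model, and a model whose contrast is left open.

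**What to change.** - **Section 8.2:** state that d=0.53 and its power apply to a within-resident mean contrast. Give the figure for the final n and the sidedness used: 0.87 for a two-sided paired t test at n=36.
- **Section 8.3 and the SAP:** estimate the SABL or dose effect within resident from the SABL and usual-light visits already scheduled, with a resident effect and a period term. State which visits enter the model.
- **Any dose slope across residents:** label it exploratory and give its own detectable effect (80% power for |r| of about 0.45 at n=36, two-sided). State that a null slope will not be read as absence of a SABL effect.

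This is a change of wording in three places and needs no new residents or data. The cost is a less favourable stated power: 0.87 in place of 0.92 for the within-resident contrast, and a visibly limited detectable effect for any across-resident slope.
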